Effects of implant Placement Depth (4 mm versus 6 mm) on crestal bone stability in Immediate Implant Placement: A Clinical Study with 1-Year Post-Restorative results

2020-06-18

Ethical permission: BEC-LSMU(R)-41

Participants in this study were scheduled for tooth extraction followed by immediate implant placement. One hour prior to the procedure, patients were administered 1 g of amoxicillin orally, which was continued at a dosage of twice daily for one week after the procedure. Teeth were extracted under local anesthesia using 4% articain with epinephrine 1:100000 (Ubistesin forte, 3M ESPE, USA), with an emphasis on minimizing trauma and avoiding flap elevation, employing root sectioning if necessary. Care was taken to preserve the marginal gingiva and papillae. Following extraction, the socket was cleaned and assessed. Osteotomies were created using the original drills in a sequence specified by the implant manufacturer. The implant was placed centrally in the mesio-distal aspect and more towards the lingual/palatal side of the socket. According to the group allocation, control group implants were positioned 4 mm below the mid-facial gingival margin, while test group implants were placed 6 mm below the gingiva. The insertion torque was recorded with manual torque wrench [13]. Anatomical or individual healing abutments were used after implant placement. Individual healing abutments were crafted chairside using original titanium temporary abutments and flowable composite (3M Supreme Filtek Flow, 3M ESPE, USA), creating critical and subcritical contours. The composite was polished meticulously. All immediate implant sites were grafted with allogenic cortical/cancellous particulate (1000-1700 micron) bone material (Rocky Mountain Tissue Bank, RMTB, USA), up to the gingival margin (Figure 3B) and healing abutments were secured on the implants with 15 Ncm torque. Postoperative instructions were provided both verbally and, in a booklet, advising patients to rinse their mouths twice daily for 2 weeks with a commercially available mouth rinse containing 0.12% chlorhexidine di-gluconate. After 4 months, the osseointegration of implants was evaluated for presence or absence of following symptoms: pain, recurrent peri-implant infections, mobility on manual palpation and continuous peri-implant radiolucency. If those symptoms were absent, implant was deemed successfully integrated and silicone impressions for final restorations were taken. Screw-retained full-contour zirconia crowns with ultra-polished subgingival areas, were delivered. The access holes were filled with Teflon tape, and while the top 1 mm was sealed with flowable composite. Individual oral hygiene instructions were provided both verbally and in booklet form. Scheduling of follow-up visits were carried out after 1 year of last dental visit.

The primary outcome was the radiologic evaluation of peri-implant MBL. Secondary outcomes implant stability in terms of primary and secondary stability measured in implant stability quotient (ISQ). Parallel intraoral radiographs with a radiovisiography (RVG) sensor (Carestream RVG 5200, Carestream Health, USA) and standard holder (Dexis IXS Digital Sensor Holder, USA) were taken after implant placement (T0), just

after delivering final resto-ration (T1) and at 1- year follow-up visit (T2). The alignment of the radiographs was verified by the image of the implant neck, which appeared as an un-distorted straight line. If the image was not in a parallel orientation, the angulation of the holder position was changed, and another radiograph was taken. ImageJ (v 1.54p, NIH, USA) software was used to analyze radiographs at T0, T1 and T2 time points. Original obtained image was enlarged 20 times for more precise calculation. The diameter of the implant was utilized to calibrate the dimensions of all radiographic images. MBL around the implant was assessed by measuring the distance from the implant-abutment junction to the initial point of bone contact on both the mesial and distal sides, and an average was determined for each implant. MBL change was calculated by subtracting the T2 values from the T1 measurements. Negative values showed bone loss, while positive values indicated bone gain. To establish intra-examiner reliability, the second and third measurements were compared, as they were taken with a one-month interval between them. The final data point used was the average of all three measurements, and the standard deviation (SD) was controlled to not exceed 0.1 mm. All radiograms were in-dependently analyzed by an experienced dentist who was blinded to the study's purpose and was not involved in the execution of the research. Primary implant stability was determined using resonance frequency analyzer (MEGA ISQ II, Megagen, S. Korea) in the buccolingual and mesiodistal direction and an average value was noted down. ISQ value was measured for each implant at the baseline followed by before the final restoration.

Statistical analysis

Sample size calculation was based on primary outcome variable crestal bone loss. G*Power was used to calculate sample size. Effect size was calculated based on the data of De Siqueira and colleagues (mean and SD of two groups: 1.03 ± 0.6 and 0.66 ± 0.38). To achieve power of 90% with an α level 0.05, minimum sample size came out to be 29 patients. To compensate for attrition rate and to accommodate possible dropouts, a total of 36 patients were enrolled, 18 in each group. The normality of the collected data was determined using the Shapiro-Wilk test. Based on normality, parametric (the t-test and paired samples t-test) or non-parametric (the Mann-Whitney U test and Wilcoxon matched-pairs signed rank test) statistical tests were employed to compare dependent variables between groups and within groups at different time points, respectively. SPSS v24 (IBM Corp., USA) was used for statistical analysis, and the significance level was set at $p < 0.05$.

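### The plan has no rule for scoring bone coronal to the implant-abutment junction, so its change formula can hide or reverse bone loss there, and the two arms may be affected unequally.

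*Combined protocol and SAP*

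**What the plan says.** The outcomes paragraph of the combined protocol and SAP defines the bone level thus: "MBL around the implant was assessed by measuring the distance from the implant-abutment junction to the initial point of bone contact", read "on both the mesial and distal sides, and an average was determined for each implant". It then gives the change, "MBL change was calculated by subtracting the T2 values from the T1 measurements", and its interpretation: "Negative values showed bone loss, while positive values indicated bone gain". A sign is defined for the change. None is defined for the level, and nothing says whether bone coronal to the junction counts as negative, zero or positive.

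The procedure paragraph sets the allocated depths from the soft tissue, not from bone: "control group implants were positioned 4 mm below the mid-facial gingival margin, while test group implants were placed 6 mm below the gingiva". It also states "All immediate implant sites were grafted with allogenic cortical/cancellous particulate", with the graft filled to the gingival margin in both arms. Crest position relative to the junction is not given for either arm at any time point.

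Under Statistical analysis, the planning data for crestal bone loss are "mean and SD of two groups: 1.03 ± 0.6 and 0.66 ± 0.38".

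**The concern.** T1 minus T2 is negative for loss only if the recorded number grows as bone recedes. That holds when bone meets the implant at or apical to the junction. When bone lies coronal to it, a plain distance shrinks as bone recedes, and the formula labels the loss a gain. If the reader records contact only on the implant, the value is 0 until bone passes the junction, and loss above it is not seen.

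In many implant studies this would mainly add noise. Here the allocated factor is the depth of the implant, so it moves the zero point of the ruler by 2 mm between arms. Graft is also placed up to the gingival margin at every site, so bone coronal to the junction is a foreseeable case. A scoring error that depends on the zero point could then appear as a treatment difference in the primary outcome. Blinding the reader and averaging three readings do not remove a systematic error of this kind.

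**Working it through.** **Inputs from the documents.** Depths are 4 and 6 mm, and change is T1 minus T2 with negative as loss. The planning difference is 1.03 − 0.66 = 0.37 mm. The plan gives no figure for this problem, so 0.37 mm serves only as a yardstick. The minimum sample size is not used.

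**Step 1: single sites.** Let x be the position of first bone contact on the implant axis, with the junction at 0, apical positive and coronal negative. The three possible scorings of change are:
- signed: x(T1) − x(T2)
- unsigned: |x(T1)| − |x(T2)|
- stopped at the junction: max(x(T1), 0) − max(x(T2), 0)

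| x at T1 (mm) | x at T2 (mm) | Signed (true) | Unsigned | Stopped at junction |
|---|---|---|---|---|
| −2 | −1 | −1.0 | +1.0 | 0 |
| −1 | +0.5 | −1.5 | +0.5 | −0.5 |
| −0.5 | +0.5 | −1.0 | 0 | −0.5 |
| −0.5 | +1 | −1.5 | −0.5 | −1.0 |
| 0 | +1 | −1.0 | −1.0 | −1.0 |

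All three agree only when bone starts at or apical to the junction.

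**Step 2: direction.** Take a site that loses L > 0 from position x. Unsigned recorded loss is |x + L| − |x|. It equals −L for x ≤ −L, 2x + L for −L < x < 0, and L for x ≥ 0. Recorded loss with readings stopped at the junction is 0, x + L and L over the same ranges. Neither ever decreases as x increases. If the crest distribution and loss are the same in both arms, placing the implant 2 mm deeper lowers x by 2 and can only reduce recorded loss or leave it unchanged. The false difference therefore favours 6 mm or is zero.

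**Step 3: size, under assumptions.** The documents do not give the following, so they are assumed:
- crest at T1 c mm below the margin, normal with SD 0.7, the same in both arms
- junction at the stated depth d, so x(T1) = crest − d
- true loss normal with mean 0.66 and SD 0.38 in both arms, borrowed from one planning group
- x(T2) = x(T1) + loss

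The simulation used 1,000,000 draws per setting. The true mean change is −0.66 mm in both arms, and the signed difference between arms was 0.00 in every setting. Cells show the 4 mm arm / 6 mm arm; gaps were computed before rounding.

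| c (mm) | Bone above junction at T1 | Mean change, unsigned | Gap | Mean change, stopped at junction | Gap |
|---|---|---|---|---|---|
| 1.5 | 100% / 100% | +0.65 / +0.66 | 0.01 | 0.00 / 0.00 | 0.00 |
| 2 | 100% / 100% | +0.63 / +0.66 | 0.03 | −0.01 / 0.00 | 0.01 |
| 3 | 92% / 100% | +0.36 / +0.66 | 0.30 | −0.15 / 0.00 | 0.15 |
| 4 | 50% / 100% | −0.28 / +0.63 | 0.91 | −0.47 / −0.01 | 0.46 |
| 4.5 | 24% / 98% | −0.52 / +0.55 | 1.06 | −0.59 / −0.06 | 0.53 |
| 5 | 8% / 92% | −0.62 / +0.36 | 0.98 | −0.64 / −0.15 | 0.49 |
| 7 | 0% / 8% | −0.66 / −0.62 | 0.04 | −0.66 / −0.64 | 0.02 |

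As a check, |x| = 2·max(x, 0) − x. With equal true change in the two arms, the unsigned gap must therefore be twice the stopped-at-junction gap, and it is.

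**Step 4: sensitivity.** With SD 0.75 and a crest at 2, 3, 4 or 5 mm, the gaps are 0.04 to 0.95 mm (unsigned) and 0.02 to 0.48 mm (stopped). With true loss of 1.03 mm (SD 0.6) on the same settings, the unsigned gap is 0.16 to 1.45 mm.

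**The case against.** A reader might infer that the plan uses an unsigned distance. It does not say so: it is silent on the sign of the level. Recording coronal contact as a negative distance fits the stated convention for change exactly and gives no bias. This stands, so the fault is a missing rule in the primary outcome, not a demonstrated misreading.

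A reader might also infer that the problem sits mainly in the 6 mm arm, or that the endpoint does favour that arm. The documents support neither as fact. With an assumed crest at 2 mm, nearly every site in both arms is affected and the gap is 0.03 mm or less. With a crest at 7 mm, few sites are affected in either arm.

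The size also rests on a link that the documents do not make. Depth is set at the mid-facial margin, while bone is read mesially and distally. The model uses one crest distance for both. That weakens the figures but not the single-site arithmetic, and the direction still follows under an equal crest distribution at the reading sites and a 2 mm shift of the junction there.

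Finally, loss of bone contact along the implant is a legitimate outcome. If that is what was meant, stopping at the junction is an endpoint choice. The conclusion should then be limited to bone loss apical to the junction, and the plan should say so. Nothing here requires a different primary landmark.

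**Conclusion.** The concern holds in a conditional form. The level has no scoring rule for bone coronal to the junction, and the stated formula, taken literally, is correct only at or apical to it. If levels were unsigned or stopped at the junction, the primary comparison could be biased towards the 6 mm arm or left unaffected, given equal true loss and the same crest distribution in both arms. Neither scoring would favour the 4 mm arm under those conditions.

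The size cannot be determined from the documents. Over the assumed crest range it runs from practically nothing to more than the 0.37 mm planning difference: at most about 0.5 mm if readings stop at the junction and about 1.1 mm if unsigned. If levels were already signed, there is no bias, and one sentence closes the point. Because this is the primary outcome and the error could create a difference where none exists, the rule should be settled before the between-arm result is interpreted.

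**What to change.** In the outcomes paragraph, define the level as a signed value on the implant axis: junction at 0, apical positive, coronal negative, no floor at 0. Apply it mesially and distally at T0, T1 and T2 in both arms. Keep first bone contact as the landmark and keep T1 minus T2, so that negative still means loss.

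Report, by arm and time point, how many sites have bone coronal to the junction. State how the existing readings were made. If they were unsigned, assign the sign from the radiographs. If they stopped at the junction, either re-read the radiographs or limit the conclusion to bone loss apical to the junction.

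The cost is a sentence or two of text and some re-reading of images already taken. Assuming one implant per patient, a full repeat is at most 36 patients × 2 sides × 3 time points × 3 readings = 648 readings. No new visits or images are needed.

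### The 29 patients claimed for 90% power do not follow from the plan's own inputs; 18 per group give about 57% power (two-sided, all 36 evaluable)

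*Combined protocol and SAP*

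**What the plan says.** The sample-size text is in the Statistical analysis section of the combined protocol and SAP.

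- Endpoint used for sizing: "Sample size calculation was based on primary outcome variable crestal bone loss".
- Effect size, from a cited study: "mean and SD of two groups: 1.03 ± 0.6 and 0.66 ± 0.38".
- Result, attributed to G*Power: "To achieve power of 90% with an α level 0.05, minimum sample size came out to be 29 patients".
- Enrolment after a dropout allowance: "a total of 36 patients were enrolled, 18 in each group".

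Because 29 is raised to a total of 36, it can only be a total and not a per-group number. The section names the t-test or Mann-Whitney U test for comparisons between groups and the paired tests for comparisons within groups over time. The procedure description has two separate arms: "control group implants were positioned 4 mm below the mid-facial gingival margin, while test group implants were placed 6 mm below the gingiva". The plan does not state whether the test is one- or two-sided, which G*Power test was selected, or what dropout rate was assumed.

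**The concern.** A standardised difference of about 0.74 is moderate to large, but roughly 15 patients per group is far too few to detect it with 90% power in a comparison of two independent groups. The paragraph gives every input needed to repeat the calculation except sidedness, so it can be checked directly.

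This paragraph is the only justification for the size of the trial, and it concerns the primary outcome. If it is wrong, the trial reports a 10% risk of missing the planned effect when the real risk is several times larger. The trial asks about crestal bone stability at two depths, so a reader who trusts the 90% figure could take a non-significant result as evidence that depth does not matter. The data could not support that conclusion.

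**Working it through.** **Inputs (Statistical analysis section).** Means 1.03 and 0.66, SDs 0.60 and 0.38, power 90%, α 0.05, equal groups, 29 in total before dropout, 36 enrolled. Sidedness is not given, so I take two-sided as the base case and show one-sided as well.

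**Effect size.**

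- Difference = 1.03 − 0.66 = 0.37 mm
- Pooled SD = √[(0.60² + 0.38²)/2] = √[(0.3600 + 0.1444)/2] = √0.2522 = 0.502
- d = 0.37/0.502 = 0.737

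**Attempt to reproduce 29.** The normal approximation for the number per group is 2(z₁₋α/₂ + z₁₋β)²/d².

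- 90% power, two-sided: 2(1.960 + 1.282)²/0.737² = 38.7 per group
- 80% power, two-sided: 2(1.960 + 0.842)²/0.737² = 28.9 per group

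The exact calculation uses the noncentral t distribution with n₁ + n₂ − 2 degrees of freedom and noncentrality d√[n₁n₂/(n₁ + n₂)]:

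| Setting | Per group | Total |
|---|---|---|
| 90%, two-sided t-test | 40 (power 0.902; 39 gives 0.895) | 80 |
| 90%, one-sided t-test | 33 (power 0.906; 32 gives 0.898) | 66 |
| 90%, two-sided Mann-Whitney (relative efficiency 3/π) | 42 | 84 |
| 80%, two-sided t-test | 30 | 60 |
| 90%, one-sided, using only the smaller SD of 0.38 | 19 | 38 |

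The last row is the most favourable independent-groups reading at 90% power, and it still exceeds 29. The stated figure is not reproduced.

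**Power of the trial as sized, at 0.37 mm.** With 18 per group the noncentrality is 0.737 × √9 = 2.21 on 34 degrees of freedom.

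| Evaluable patients | Two-sided | One-sided |
|---|---|---|
| 18 + 18 | 57.4% | 69.9% |
| 16 + 16 | 52.3% | 65.2% |
| 14 + 15 | 48.1% | 61.3% |
| 29 + 29 (if 29 were meant per group) | 78.7% | 87.0% |

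A simulation with the unequal SDs and 18 per group gave 57.6% for Student's test and 57.0% for Welch's, so pooling the SDs does not drive the result.

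**Detectable difference with 18 per group, two-sided.**

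- 90% power: d = 1.112, that is 1.112 × 0.502 = 0.56 mm
- 80% power: d = 0.961, that is 0.961 × 0.502 = 0.48 mm

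With only 29 patients, 90% power would need d of about 1.25, against the plan's 0.737.

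**Expected precision.** The 95% confidence interval half-width is t₀.₉₇₅ × 0.502 × √(1/n₁ + 1/n₂).

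- 18 + 18: 2.032 × 0.1674 = 0.34 mm
- 14 + 15: 2.052 × 0.1866 = 0.38 mm

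Both are about the size of the 0.37 mm difference the trial was planned to detect.

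**The case against.** The best defence of 29 is that a paired calculation was run. A paired t-test on the stated SDs with a within-pair correlation of 0.35 has an SD of differences of √(0.5044 − 2 × 0.35 × 0.60 × 0.38) = 0.587 and a standardised difference of 0.37/0.587 = 0.630. It then needs exactly 29 pairs for 90% power, two-sided (29 gives 0.906; 28 gives 0.895). One-sided, a correlation of 0.15 also gives 29. This may explain where the number came from, but it does not justify it. The plan states no correlation, the two depths are in different patients, and paired tests are kept for changes within a group.

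Another possible origin is a per-group figure for 80% power (28.9 by the normal formula) read as a total at 90%. The exact t calculation, however, gives 30 per group at 80%. The documents cannot settle which explanation is right, and nothing here depends on it. Nor is the odd total much evidence by itself: an odd minimum before a dropout allowance is untidy, not wrong.

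Three qualifications stand. The 57% figure assumes a two-sided test and all 36 patients evaluable. It also takes the cited study's SDs as applying to this trial's change from final restoration to one year, which cannot be checked here. Last, the plan makes no equivalence claim, so a misreading of a non-significant result is a risk and not something the text commits to.

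**Conclusion.** The concern holds. On the plan's own inputs, 90% power needs 80 patients (two-sided) or 66 (one-sided), not 29. The two-sided requirement is understated by a factor of 80/29, about 2.8. With all 36 evaluable and a two-sided test, power at 0.37 mm is about 57%, so a real difference of the planned size would be missed about 43% of the time instead of 10%. A one-sided test would raise power to about 70%, still well short of the claim. Any dropout lowers these figures.

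The conclusion rests on independent groups, as the plan describes, and on the stated means and SDs. It does not depend on sidedness, on the choice between t-test and Mann-Whitney, or on how 29 arose. This must be corrected, because the trial relies on the stated power to justify its size.

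**What to change.** Replace the sample-size sentences with text that:

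- gives the test and sidedness, and says that 40 per group would be needed for 90% power at 0.37 mm (SDs 0.60 and 0.38, two-sided 5%);
- says that the enrolled 18 per group give about 57% power at that difference, about 48% with 29 completers, and 90% power only for about 0.56 mm;
- states the dropout rate assumed.

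Two reporting changes should accompany the correction. Make the between-group mean difference with its 95% confidence interval the primary result, and say how that interval will be given if the normality check leads to the Mann-Whitney test. State that a non-significant p-value will not be read as equal bone stability.

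The cost is one paragraph of protocol and SAP wording and a less favourable power statement. The correction needs no extra patients and no change to treatment or measurements.

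### A restored patient without a one-year film drops out of the T1–T2 comparison although T0 and T1 bone levels are measured, which can bias the depth comparison; extra enrolment does not prevent this

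*Combined protocol and SAP*

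**What the plan says.** All references are to the Combined protocol and SAP, whose sections are unnumbered.

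- **Attrition.** The Statistical analysis section gives the target as "To achieve power of 90% with an α level 0.05, minimum sample size came out to be 29 patients", followed by "To compensate for attrition rate and to accommodate possible dropouts, a total of 36 patients were enrolled, 18 in each group". It states no dropout rate. Neither this section nor the rest of the document gives an analysis set, a method for missing values, a sensitivity analysis, or a plan to report why patients were lost.
- **Outcome.** The paragraph on outcomes and radiographs, just before that section, has films read at T0 (placement), T1 (crown delivery) and T2 (one year). It then defines the outcome: "MBL change was calculated by subtracting the T2 values from the T1 measurements".
- **Test.** "Based on normality, parametric (the t-test and paired samples t-test) or non-parametric" tests are used, with Mann-Whitney U as the non-parametric comparison between groups. No model uses T0 or T1 as a covariate or as a repeated measure.

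**The concern.** A patient who receives a crown but has no T2 film has no T1–T2 change. Neither the t-test nor the Mann-Whitney U test can include that patient. The plan does not state this exclusion; it follows from how the outcome is defined. The patient's T0 and T1 levels, which may carry information about the missing value, then play no part in the depth comparison.

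Enrolling more patients restores the count of completers but does not make them representative. If patients with more early loss tend not to return, and this acts unequally in the two arms, the arm that loses them looks better than it should. At stake is the estimated effect of depth on bone, which is the trial's main question.

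The point is confined to restored implants lost after T1. An implant that fails the 4-month check has no T1 level and raises a different question.

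**Working it through.** **1. The plan's own figures.** Inputs from the Statistical analysis section are "mean and SD of two groups: 1.03 ± 0.6 and 0.66 ± 0.38", power 90% and α 0.05.

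- Planned difference: 1.03 − 0.66 = 0.37 mm.
- Root-mean-square SD: √[(0.60² + 0.38²)/2] = 0.502 mm.
- Standardised effect: d = 0.37/0.502 = 0.737.
- n per arm, two-sided, normal approximation: 2(1.960 + 1.282)²/0.737² ≈ 38.7, so 39 at 90% power.
- At 80% power: 2(1.960 + 0.842)²/0.737² ≈ 28.9, so 29 per arm.

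The stated 29 is therefore not reproduced as a total at 90% power. That is a separate matter. It bears here only on whether 36 − 29 = 7 (7/36 = 19.4%) can be read as a planned dropout allowance. Below, 7 is used as an illustrative number of losses.

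**2. Who contributes to the test.**

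| Patient | T0 | T1 | T2 | T1–T2 change | In the planned between-group test |
|---|---|---|---|---|---|
| Restored, attends T2 | yes | yes | yes | yes | yes |
| Restored, misses T2 | yes | yes | no | none | no |

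**3. When dropping the second row causes bias.** Call loss from T0 to T1 early and loss from T1 to T2 late. If non-return depends on early loss, the expected bias of the completer difference is

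bias = ρ × SD(late) × Δ,

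where ρ is the within-arm correlation of early and late loss. Δ is the difference between arms in how far selection shifts the completers' mean early loss, in SD units. The bias is zero if ρ = 0 or if the shift is equal in both arms (Δ = 0).

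**4. Size under assumed inputs.** None of these inputs is in the documents: SD 0.5 mm in each period (close to the 0.502 above), no true difference, and probability of loss proportional to exp(1.5 × standardised early loss). There were 18 patients per arm and at least 4,000 simulated trials per setting. Monte Carlo error is about 0.19/√4000 = 0.003 mm.

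| 7 lost, split between arms | Bias, ρ = 0 | Bias, ρ = 0.3 | Bias, ρ = 0.5 | Share of 0.37 mm (ρ 0.3 to 0.5) |
|---|---|---|---|---|
| 4–3 | about 0 | 0.01 mm | 0.02 mm | 3% to 5% |
| 5–2 | about 0 | 0.03 mm | 0.05 mm | 8% to 14% |
| 7–0 | about 0 | 0.07 mm | 0.11–0.12 mm | 19% to 32% |

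The formula gives a consistency check. In the 7–0 row, 0.11/(0.5 × 0.5) = 0.44 SD for Δ. With ρ = 0.3 this predicts 0.3 × 0.5 × 0.44 = 0.07 mm, as simulated.

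With fewer losses, all in one arm, and ρ = 0.5, the bias is 0.05 mm for 3 lost and 0.08 mm for 5. The standard error of the difference is 0.17–0.19 mm. The completer t-test's type I error is 5–6% in the split-loss settings and about 9% at 7–0 with ρ = 0.5.

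**5. A second mechanism, large samples.** Here the true difference was −0.37 mm, 19.4% were lost overall, ρ ran from 0 to 0.7, and the log-odds of loss rose by 0 to 2 per SD of early loss.

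- Same early loss and same mechanism in both arms: bias about 0.
- Same mechanism, early loss differing by 0.37 mm between arms, ρ of 0.3 or more: about 0.01 to 0.06 mm, in either direction.
- Loss also depending on early loss in one arm only: up to about 0.14 mm, at ρ = 0.7 with 6.5% lost in one arm and 32.5% in the other.

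**6. Using the earlier readings.** An estimate that uses the early readings of all patients had bias of about 0.00 mm in every setting of steps 4 and 5. In the 18-per-arm runs its standard error was within about 5% of the completer test's, for example 0.193 against 0.191 mm with 7 lost from one arm at ρ = 0.5. With nobody lost the two estimates coincide. The lack of bias follows from the simulated mechanism, in which loss depends only on observed early loss.

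**The case against.** The strongest reply is that a missing plan for missing data is not itself a bias. Loss related to early bone loss is not enough. Early loss must also predict late loss, and the process must differ between arms. The documents give no evidence on either condition, and with losses split fairly evenly the bias is a small fraction of the standard error. This stands, and it is why the point says *can* bias.

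Three stronger readings are tempting, and the documents do not support them.

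- **That the plan budgets for 19% loss after T1.** No rate is stated; 7 is only 36 minus 29. Any allowance would also have to cover implants that fail the 4-month check. If 29 was in fact a per-arm figure, a total of 36 contains no allowance at all.
- **That patients have no contact between crown delivery and T2, so anyone with trouble disappears.** The treatment description mentions follow-up scheduled a year after the last visit. It is silent on interim contact and does not exclude it.
- **That the readings in hand fully correct the problem.** They do so only if non-return depends on observed bone levels. A patient who leaves because of trouble arising after T1 is lost for an unobserved reason, and the model does not repair that.

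A last objection is that a repeated-measures model assumes approximate normality, whereas the plan has a non-parametric branch. That is fair, and the fix has to provide for it. It does not rescue the completer analysis, because Mann-Whitney U drops the same patients.

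**Conclusion.** The point holds in conditional form. The text establishes three things: extra enrolment is the only provision for attrition, the T1–T2 comparison cannot use a restored patient without T2, and that patient's T0 and T1 levels are measured.

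A reader might infer that the depth comparison *is* biased, or that the bias is about a third of the target effect. The documents support neither. The larger figure (0.07–0.12 mm) needs all 7 losses to fall in one arm. A 5–2 split gives 0.03–0.05 mm, a 4–3 split 0.01–0.02 mm, and zero correlation gives none. All of these rest on an assumed SD of 0.5 mm, correlations of 0.3 to 0.5 and an assumed loss mechanism; other assumptions change the size and can reverse the direction.

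This is a worthwhile and inexpensive improvement to the analysis, not a demonstrated flaw in the result.

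**What to change.** In the Statistical analysis section, before T2 results are examined:

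1. Estimate the T1–T2 group contrast from a repeated-measures model on MBL at T0, T1 and T2, with visit, group, visit × group and unstructured covariance. Include all patients in their allocated group, whether or not T2 was obtained.
2. Report the completer t-test as a sensitivity analysis, or the Mann-Whitney U test if residuals are clearly non-normal.
3. Report the number lost and the reasons by arm. This is the only information on mechanisms that the model cannot address.

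**Cost.** A few lines of SAP text, one mixed model that can be fitted in the planned SPSS v24, and a record of why each patient missed T2. No extra visits, films or patients are needed. If everyone attends T2, the estimated contrast is unchanged.

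**Downside.** The analysis is slightly more complex. It assumes approximate normality and that missingness depends only on observed bone levels. It does not correct loss caused by unobserved problems after T1.
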